## **Objective**

We intend to demonstrate the feasibility of using a nasal endoscope to perform intraoperative angiography of surgical field, with the goals to evaluate anatomical landmarks and tumor characteristics during skull base surgery and publish a technical note.

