## **Proposal**

Based on the positive experience of our Pilot study where ICG accurately demonstrated visualization of perfusion of the pedicled flap posterior nasal arteries and mucosal flap during endoscopic endonasal approaches, we now propose a study in which we will administer ICG during routine EEA for cranial base pathologies in which optic canal decompression, intradural tumor dissection, or dissection of tumor around the internal carotid artery will be necessary.

We anticipate needing no more than thirty-five patients to obtain the necessary information and will either seek further IRB approval or terminate this feasibility study if the necessary information cannot be obtained by the thirty-fifth patient. All surgeries will be performed in a team with [name] (Neurological Surgery) and either [name] (Otolaryngology) or [name] (Otolaryngology). We will use the Storz nasal endoscope, which is already purchased and routinely used at The Ohio State University (OSU), modified as described by Litvack *et al.* to visualize the proposed real-time angiograms. These modifications include a custom xenon light source that produces both the standard white light as well as near-infrared (690-780 nm wavelength) light and a selectable near-infrared filter for the nasal endoscope, both of which will be provided by

Karl Storz free of charge. We intend to administer ICG, which is already widely used during open neurosurgical procedures, to identify anatomical landmarks (such as vascular structures leading to the optic canal and internal carotid arteries) and tumor characteristics (such as tumor vascularization, tissue differentiation, and vessel encasement) during skull base surgery at different stages of endonasal cranial base surgery and tumor dissection: before intradural dissection and during tumor dissection.

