## **Data Collection**

Specifically, patient demographic/clinical information to be included in this feasibility study will include:

- a. Age
- b. Gender
- c. Race
- d. Vital Signs
- e. Diagnosis
- f. Duration of Disease
- g. Brief Medical History
- h. Description of Surgical Approach
- i. Description and Images of Intraoperative Angiography

Medical imaging data to be presented will include pre- and post-operative CT and MR studies in addition to intraoperative angiography and intraoperative endoscopic images of the surgical site.

If, during the course of the procedure, the operator determines that it would be in patient's best interest to prematurely abort the procedure due to unforeseen events, it will be under the discretion of the PI to use the data from the prematurely aborted procedure. If patient has a second procedure after the first procedure was prematurely aborted, it is up to the PI discretion to re-dose patient with the ICG dye and complete the study procedures and collect study data from the second procedure. The PI may decide whether to use the data from the first procedure in this circumstance. ICG dye half-life is 3-4 minutes and does not pose a threat of overdosing.

In summary, this novel technique for performing real-time endoscopic intranasal angiography could substantially improve the safety of surgery by precisely locating the optic canal and internal carotid arteries; by providing additional information on tumor characteristics such as vascularization and vessel encasement.

This information may prompt further surgical action to avoid the complications associated with optic canal decompression, dissection near the internal carotid and tumor dissection. Presentation of this feasibility study in the literature will likely lead to wide acceptance and implementation of this technique due to the highly useful information it will yield as well as its high degree of feasibility, as institutions performing EEA procedures already possess the materials necessary to perform it.

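### Does the claim that endonasal centres already own the equipment undermine the feasibility study, given that its own near-infrared parts come from the manufacturer?

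*Protocol*

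**What the plan says.** Three places in the Protocol bear on this point.

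- **Objective.** The aim is technical: "We intend to demonstrate the feasibility of using a nasal endoscope to perform intraoperative angiography of surgical field". The planned output is a technical note. Nothing here refers to what equipment other hospitals hold.
- **Proposal.** The nasal endoscope is one "which is already purchased and routinely used at The Ohio State University (OSU), modified as described by" an earlier published report. The first addition is then named: "These modifications include a custom xenon light source that produces both the standard white light as well as near-infrared (690-780 nm wavelength) light". The second is a filter that can be switched in for near-infrared viewing. The endoscope's manufacturer supplies the two parts at no cost.
- **Data Collection, closing summary.** Publication is expected to bring wide adoption "due to the highly useful information it will yield as well as its high degree of feasibility". The reason given for the second of these two grounds is that "institutions performing EEA procedures already possess the materials necessary to perform it".

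**The concern.** Feasibility is the only question this study asks, so a sentence that says why the technique is highly feasible deserves a close look. The reason offered is that endonasal centres already hold everything needed. The Proposal section indicates that the study site, itself such a centre, does not: it has the endoscope, while the two parts that make near-infrared imaging possible come from outside.

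If the sentence went unchanged into the technical note, surgeons elsewhere could conclude that they need buy nothing new. The evidence would in fact come from a specially adapted instrument. The manufacturer's support would also go unmentioned at the one point where it bears on the claim. What would be at stake is the reach of the conclusion, and openness about the conditions under which it was obtained.

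**Working it through.** No arithmetic applies. The Protocol gives no figure that depends on equipment ownership, and the cap of thirty-five patients is not derived from it. The check is a comparison of the text.

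**Step 1: is there a conflict?** The Proposal section names three optical components.

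| Component | Status in the Proposal section |
|---|---|
| Nasal endoscope | Already bought and in routine use at the site |
| White and near-infrared light source | To be supplied by the manufacturer, free |
| Selectable near-infrared filter | To be supplied by the manufacturer, free |

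The closing summary speaks of the necessary materials without qualification. One could read that as the endoscope and the dye alone, since the Proposal section describes ICG as already in wide use in open neurosurgery. That reading is strained, because the adaptations are introduced as the means of seeing the angiograms and so are necessary on the Protocol's own account. The conflict is real.

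**Step 2: how far does it go?** The Protocol has no information on what other institutions own. It also does not say what equipment the pilot study used, or who owned it. The sentence is therefore unsupported and out of line with the Proposal section, but it is not shown to be false for every centre. Counting two components of three as missing measures nothing, because the term materials is undefined and the denominator depends on what one chooses to list.

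**Step 3: what depends on the sentence?** Each element of the plan can be taken in turn.

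- Objective: performing angiography with the endoscope. This can be shown whoever supplied the light source and filter.
- Eligibility: set by the type of surgery, age, allergy history, and pregnancy or nursing. Unaffected.
- Study procedures: the Proposal section already specifies the adapted instrument. Unaffected.
- Sample size: at most thirty-five patients, with further ethics approval or termination if the information has not been obtained by then. Unaffected.
- Data items a to i: unaffected. Item i, the account and pictures of each angiogram, is where an angiogram that failed for technical reasons would be described.
- Adverse events and risk assessment: unaffected.

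**Step 4: what does the sentence itself support?** It supports a prediction of uptake that has two grounds, the value of the information and ease of adoption. Equipment ownership is the reason for the second only. If it is struck out, the first ground and the study question both remain.

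**The case for a change.** The strongest case for a change is that the contradiction lies between two current sections and needs no outside source to see. Ownership of the materials is the only reason offered for high feasibility. The sentence is explicitly about presenting the study in the literature, so the risk that it shapes the technical note is not fanciful. Correcting it would cost one sentence, and one further item per case could record equipment faults or trouble switching between white and near-infrared light.

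Part of this stands. The wording is wrong for the site as the Proposal section describes it, and a careful author would limit it to the endoscope and the dye.

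The rest does not carry through to a change of plan. Nothing in the Protocol says the sentence will be reproduced in the publication. The added parts and their free supply are not concealed: they are stated openly where the equipment is described, so a report of the methods would naturally carry them. Recording equipment faults case by case is a separate preference about data collection. It does not follow from an overstatement about who owns what, and item i already leaves room for it.

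**Conclusion.** The inconsistency is confirmed, and no change to the plan is needed. It is confined to one forward-looking sentence in a closing summary and touches only a remark about wider uptake. It leaves the technical feasibility question in the Objective section intact, and no patient, procedure, recorded variable or analysis would differ if the sentence were reworded or deleted. Its numerical size is zero.

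This rests on two assumptions. The first is that feasibility keeps the meaning given in the Objective section, namely that the angiography can be performed, and is not redefined as availability of equipment at other centres. The second is that the technical note describes the instrument as the Proposal section does, including the manufacturer's supply of the light source and filter. Both are what one would ordinarily expect of authors following this Protocol. On that footing, any statement about uptake is properly read as applying to centres with equivalent near-infrared equipment.
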